9 QUALITY CONTROL AND QUALITY ASSURANCE

AIM 1:

Interviews will be audiotaped and transcribed verbatim for content. We will conduct analyses concurrently with ongoing interviews, if timing permits, to inform subsequent data collection and analysis. We will use a preliminary coding scheme based on the TDF and prior work by Huijg et al.,⁴¹ and Birken et al.,⁷⁶ consisting of a three step process including: 1) coding affirmative and negative utterances regarding ADT use as localized treatment into TDF domains, 2) collecting responses across respondents into themes (e.g., "ADT prevents cancer spread" into a 'ADT is beneficial' theme, "urologists should be able to treat patients as they wish" into a 'Physician autonomy' theme), 3) tallying the total number of mentions per theme, as well as conflicting beliefs within a theme (e.g., ADT is good vs. ADT is bad), according to the TDF domains, with particular emphasis on those included in our conceptual model. Study interviewers and qualitative analysts will both independently review and code transcripts and meet regularly to compare coding results until reaching agreement on code definitions and establish the reliability of the coding process (>80% simple agreement). During this process, study investigators and interviewers will also meet to categorize the codes into TDF domains, identify emerging themes, and document ongoing data interpretation in memos. Once data are coded, we will use QSR NVivo software to organize the data. Drs. [name] and the research team will meet regularly to discuss code summaries and memos, developing findings with a focus on informing the Aim 2 discrete choice tool. At the end of this aim we will have identified the highest frequency themes and themes with conflicting provider and patient beliefs across TDF domains for de-implementing ADT.

AIMS 2 AND 3: tbd

10 STATISTICAL CONSIDERATIONS

Please see above for information on qualitative analysis.

PILOT OUTCOMES

Primary Outcome Measures

A. Feasibility – Site level

- Title: Percentage of approached pilot sites with Medical Center Director approval to implement the intervention (Order Check (OR) or Progress Note/Patient Handout (SC))
 - Description: The percentage of pilot sites asked to participate that received MCD approval to implement the intervention (Order Check or Progress Note/Patient Handout)
 - Time frame: Within 1 month.
- Title: Percentage of director-approved pilot sites with intervention implementation.

- Description: The percentage of approved pilot sites with fully operationalized intervention within the site. Depending on randomization arm, this includes either health factor placement or script assignment prior to at least one patient visit.
- Time frame: Within 3 months of approval.

B. Feasibility – Clinic level

- Title: Percentage of total pilot site clinics with intervention implementation.
- Description: The percentage of clinics at approved pilot sites with at least 1 health factor assigned and/or at least 1 progress note assigned to a provider. Clinics may include Urology, Medical Oncology, and Radiation Oncology.
- Time frame: Within 3 months of intervention implementation.

Secondary Outcome Measures

A. Reach

- Title: 1.00 - The percentage of providers prescribing ADT for prostate cancer sent an information sheet who did not opt out of the study.
- Description: The percentage of providers in the study prescribing ADT for prostate cancer sent an information sheet who remained in the study.
- Time frame: Within 6 months of intervention.

B. Penetration

- Title: Percentage of SC intervention clinic notes assigned to providers that were signed.
- Definition: Percentage of clinic notes assigned to ADT providers by the study team that were successfully used by providers (signed and became part of EMR).
- Time frame: Within 6 months of intervention.
- Title: Percentage of OR intervention order checks justified.
- Definition: The number of low-value ADT orders with justification / the total number of low-value ADT orders placed.
- Time frame: Within 6 months of intervention.

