1 BACKGROUND/SCIENTIFIC RATIONALE

A. BACKGROUND & SIGNIFICANCE

A1. Evidence for castration as prostate cancer treatment

Because prostate cancer cells are dependent on androgens, i.e., testosterone, depriving them of this hormone through castration can improve clinical outcomes, for some patients.¹ The highest levels of evidence for chemical castration with androgen deprivation therapy (ADT) injections to treat prostate cancer occur in two scenarios: 1) high risk localized disease in combination with radiation therapy, and 2) metastatic cancer with spread to bones or other organs causing symptoms.²⁻⁴ However, a significant amount of castration in Medicare and integrated delivery systems (e.g., VA), occurs outside scenarios where high levels of benefit exist.^{5,6} For example, using castration for the primary treatment of localized prostate cancer is likely ineffective and harmful, yet remains common in VA with five-fold variation across facilities (Figure 1). Neither long-term studies nor current guidelines support castration as primary treatment for localized prostate cancer.^{1,3,4} Many times, this castration is continued indefinitely. Even in cases of metastatic prostate cancer without symptoms, an American Society of Clinical Oncology Panel could not make a recommendation for treatment with ADT until symptoms of disease progression (e.g., bone pain) occur due to a lack of an overall survival advantage for those treated early.⁷

A2. There is a disconnect between the value and use of castration in prostate cancer

A2.1 *Surgery to remove testicles is no longer needed for castration*

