The majority of ADT is prescribed by urologists across all stages of prostate cancer.²⁸ Therefore, this proposal will focus on urologists and their patients. Our preliminary data (Section **B1**) indicate thousands of men are at risk of ongoing low value castration, especially when it comes to castration for localized disease, with tremendous variation across integrated delivery system facilities. Indeed, this calls for effective deimplementation strategies grounded in an understanding of context, provider preferences, and evidencebased behavior change techniques.²⁹⁻³¹ *Moreover, a significant scientific and clinical knowledge gap remains in prioritizing which barriers to stopping castration in low value settings need to be targeted for effective de-implementation.* While a major focus in this study pertains to barriers, and prioritizing and overcoming barriers, facilitators for stopping ADT that are transferable across settings also need to be considered. In addition, using a discrete choice experiment (Section **C2.1**), we will be able to prioritize both positive (facilitators, preferences) and negative factors (barriers) to guide theory-based de-implementation strategies as a promising stakeholder-based approach applicable to other low value cancer care.

A4. The benefits of unlearning ineffective, low-value clinical practices and ties to behavior change

Unlearning routinized clinical practices is challenging even if they are no longer or never were considered effective.^{32,33} This is particularly true when it comes to treating patients with cancer

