7 DATA COLLECTION AND MANAGEMENT PROCEDURES

AIM 1: Only data from VA databases will be collected for participant identification and screening purposes. This data will be collected by the VA study data manager.

PROVIDERS:

For the semi-structured provider interviews, we will sample up to 20 VHA urologists from VHA facilities with the highest and lowest use of castration as primary treatment. We will use preliminary data from [name] CDA but then update the data using CDW Oncology data for the years 2016 and 2017 once our DART application is approved. We are also applying for access to Medicare claims data from VA Information Resource Center (VIReC) to validate we are not missing unidentified treatment with surgery or radiation therapy outside VHA. We plan to pull Medicare data on up to 20,000 patients. We will identify Urology Chiefs at each site using lists of providers from the most recent Federal Practitioner directory and national urologist email listserv. If possible, we will use CDW data to identify providers who meet the criteria of having experience caring for patients on ADT.

PATIENTS

We will use VA cancer registry data for years 2016 and 2017 to identify patients at high outlier sites on primary ADT for prostate cancer. Patients will be ineligible if they have dementia or other significant mental impairment noted in their medical record.

ACCESS TO DATA:

All identifiers, including interview recordings, will be stored in access restricted folders on VA servers behind the VA firewall. Only key study team members added to the AAVA IRB approved protocol personnel list will have access to data files containing PHI/PII. All personal identifiers will be stripped from the written verbatim transcripts of the interviews. Subjects will be instructed at the start of the interview to refrain from mentioning names of colleagues or from identifying the medical center.

DATA SAFETY MONITORING PLAN (DSMP):

[name] will be responsible for reporting all adverse events that might arise during the course of the study to the University of Michigan and the Ann Arbor Veterans Affairs Health System IRB. Adverse Events during this study would likely consist only of breaches in confidentiality. The following precautions have been taken to prevent this. However, should such breaches occur, [name] will report these occurrences to the overseeing IRBs within 48 hours.

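### Does the clinic-level feasibility outcome need a written rule for which clinics count, so that a clinic with no target patient is not scored as a failure?

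*Combined protocol and SAP*

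**What the plan says.** Section 10, Pilot Outcomes, lists three primary outcomes: two at site level and one at clinic level. The clinic-level Description is "The percentage of clinics at approved pilot sites with at least 1 health factor assigned and/or at least 1 progress note assigned to a provider". It adds "Clinics may include Urology, Medical Oncology, and Radiation Oncology", and the time frame is "Within 3 months of intervention implementation". The denominator is therefore limited to approved sites and three candidate specialties are named, but no rule turns these into a fixed list. No minimum ADT volume is set, and no eligible patient or prescriber is required.

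The second site-level outcome explains what being operational means: "Depending on randomization arm, this includes either health factor placement or script assignment prior to at least one patient visit". A separate secondary outcome, Penetration, has a 6-month window and asks whether assigned notes were "successfully used by providers (signed and became part of EMR)".

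Nothing elsewhere adds a rule. Section 7 says that Aim 3 runs at 4 VA sites, Section 6 describes the two strategies in concept, and Section 9 leaves quality control for Aims 2 and 3 to be determined. No target percentage, decision threshold or test is attached to the clinic-level outcome.

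**The concern.** If a health factor or note can be assigned only when a target patient has been identified, a clinic without one in the 3 months has nothing to assign. It then enters the denominator as not implemented, just like a clinic where the team tried and failed.

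Section 1 makes such clinics plausible. In A3 it says "The majority of ADT is prescribed by urologists across all stages of prostate cancer". In A1 it counts ADT for "high risk localized disease in combination with radiation therapy" among the uses with the strongest evidence, so much of the ADT given alongside radiation would not be a target of the pilot. Oncology clinics might have few relevant patients.

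What would be at stake is interpretation. The pilot prepares a full-scale trial, and a low clinic percentage could be read as failed roll-out outside Urology when those clinics simply had no one to whom the intervention applied. A list left open could also be settled after the results are known. And if only one clinic were listed per site, the outcome would come close to repeating the site-level one.

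**Working it through.** The plan states no figure for this outcome, so there is nothing to reproduce. The arithmetic shows only how far the result could move.

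**Inputs.** From the documents: 4 sites (Section 7), three named specialties and a 3-month window (Section 10). Assumed: one clinic per specialty per site (4 × 3 = 12), all sites implementing, every Urology clinic with an eligible patient, every eligible patient receiving an assignment, and a Poisson number of eligible patients with mean m per 3 months in each of the 8 other clinics.

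**Expected result under perfect delivery.** Share = [4 + 8(1 − e^(−m))]/12. The chance that at least one of the 8 clinics is empty is 1 − (1 − e^(−m))^8.

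| m | e^(−m) | Expected share | At least one of 8 empty |
|---|---|---|---|
| 0.5 | 0.607 | 59.6% | 99.9% |
| 1 | 0.368 | 75.5% | 97.5% |
| 2 | 0.135 | 91.0% | 68.8% |
| 3 | 0.050 | 96.7% | 33.5% |
| 5 | 0.007 | 99.6% | 5.3% |

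The shortfall is large at m of 1 or less and slight at 3 or more. The documents do not place m anywhere on this scale. A majority share of prescribing for urologists says nothing about absolute numbers in other clinics, and it is not specific to low-value ADT.

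**Extreme case.** If only the 4 Urology clinics have patients and all are implemented, counting every clinic gives 4/12 = 33.3% (exact 95% interval 9.9 to 65.1). Counting only clinics with a patient gives 4/4 = 100% (39.8 to 100). One clinic in 12 moves the figure by 100/12 = 8.3 points. At this scale the clinic-by-clinic table carries the information, and the percentage adds little.

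**Is a patient visit needed to score positive?** Set side by side, the definitions do not say so. The clinic-level outcome counts assignment, and the site-level text places assignment before a visit. An assignment made inside the window for a later visit would count. The signed-note criterion belongs to Penetration, which separates assigned notes from signed ones, so it does not show that assignment needs a visit. That an identified patient is needed is a fair inference, no more.

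**Overlap with the site-level outcome.** With k clinics listed at each of 4 approved sites, 3 of which implement, and at least one positive clinic per implementing site, the result lies between 3/(4k) and 3k/(4k):

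- k = 1: exactly 75%
- k = 2: 37.5% to 75%
- k = 3: 25% to 75%

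The two outcomes coincide only at k = 1, whereas three specialties are named. Even then it must be assumed that assigning a script (site level) and assigning a note (clinic level) are the same event, and that the two 3-month clocks, one from approval and one from implementation, agree.

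**Would a different rule gain anything?** Fixing a list and keeping all listed clinics in the denominator leaves an empty clinic scored as not implemented; the primary figure is not corrected. Listing every clinic in the three specialties could make it worse, because the present wording allows a clinic with no role to be left out. Restricting the denominator to clinics with an identified patient has its own cost: if finding patients is part of delivery, a clinic where that step failed would drop out and the failure would be hidden.

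**The case for a change.** The strongest argument for a change is that the plan uses opportunity-based denominators elsewhere in Section 10. The order-check outcome divides by low-value ADT orders placed, and Reach is limited to ADT prescribers who were sent an information sheet. The clinic-level outcome is primary and has no such limit. The same facts could yield 33% or 100% according to a list that need not be fixed in advance. The 3-month clock also starts at implementation, so clinics at an approved site that never implements have no start date although they belong to the denominator.

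Part of this stands. The list is not fixed, and settling it per site before the window opens is good practice. Reporting clinics listed, clinics with a patient eligible for assignment, and clinics with an assignment would separate lack of patients from lack of delivery. But these are steps that analysts of a four-site pilot take anyway. Clinics at a non-implementing site are also readily handled: they are in the stated denominator, have no assignment, and so count as not implemented.

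The ease of a data query should not be overstated either. The Section 7 statement that "we will use CDW data to identify providers who meet the criteria of having experience caring for patients on ADT" is conditional on feasibility in its own sentence, belongs to Aim 1, and concerns providers, not clinics.

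**Conclusion.** No change to the plan follows. The observation is correct as far as it goes: Section 10 names three specialties without fixing which clinics enter the denominator, and a clinic with no target patient could be counted as not implemented. This is unwritten detail in a descriptive pilot measure, of a kind that analysts fill sensibly when they list clinics and tabulate counts by site. No decision rule depends on the percentage, so no formal conclusion can go wrong.

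The size is unknown. Under the assumptions above, perfect delivery would show as anything from 59.6% (m = 0.5) to 99.6% (m = 5), with 33.3% as the extreme if only Urology had patients. All of these rest on assumed clinic numbers and patient flow, and on the inference that assignment requires an identified patient. If assignment does not, the distortion weakens and only the unlisted clinics remain. The conclusion would need revisiting if a success threshold or a go/no-go rule for the full-scale trial were attached to this percentage.

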11 REGULATORY REQUIREMENTS

11.1 Informed Consent

- *The AAVA IRB has granted waivers of written informed consent and HIPAA authorization for Aim 1 of this study.*
- *VA providers and patients will be sent a study Information Sheet and verbal consent will be obtained by study staff and interviewers during recruitment calls and at the start of the interview.*

11.2 SUBJECT CONFIDENTIALITY

- *Confidentiality will be protected by restricting access to identifiable research data to key authorized study personnel only. In particular, data*

will be stored on VA servers and in study folders that can only be accessed by specified study personnel. We will maintain an electronic list of potential participants so we can invite them to participate. The digital recordings will be stored in electronic files with filenames that indicate only generic roles and facility ID. A written verbatim transcript will be created for each participant, but all personal identifiers will be stripped from the transcript. Subjects will be instructed at the start of the interview to refrain from mentioning names of colleagues or from identifying the medical center. The transcripts and digital recordings will be stored in access-limited files in a project specific folder maintained on a VA server behind the VA firewall. All study data will be accessible only by approved study staff.

- *Data for the Aim 2 DCE survey is collected anonymously.*
- *The following UM study team members are also listed on the VA IRB and will have access to identifiers: [name], [name], [name], [name].*
- *Access to personally identifiable information is required for recruitment purposes, to confirm diagnoses and eligibility and to verify contact information. Access to protected health information is required to fulfill the Aims of this study.*
- *A Certificate of Confidentiality is not required for this study.*

11.3 Unanticipated Problems¹

- [name] will be responsible for reporting all adverse events that might arise during the course of the study to the University of Michigan and the Ann Arbor Veterans Affairs Health System IRB. Adverse Events during this study would likely consist only of breaches in confidentiality. As outlined above, precautions have been taken to prevent this. However,

¹ The Office for Human Research Protections (OHRP) considers unanticipated problems involving risks to subjects or others to include, in general, any incident, experience, or outcome that meets **all** of the following criteria:

- unexpected (in terms of nature, severity, or frequency) given (a) the research procedures that are described in the protocol-related documents, such as the IRB-approved research protocol and informed consent document; and (b) the characteristics of the subject population being studied;
- related or possibly related to participation in the research (in the guidance document, possibly related means there is a reasonable possibility that the incident, experience, or outcome may have been caused by the procedures involved in the research); and
- suggests that the research places subjects or others at a greater risk of harm (including physical, psychological, economic, or social harm) than was previously known or recognized.

An incident, experience, or outcome that meets the three criteria above generally will warrant consideration of substantive changes in order to protect the safety, welfare, or rights of subjects or others.

should such breaches occur, [name] will report to the UM IRB according to the standard reporting schedule listed here:
<https://az.research.umich.edu/medschool/guidance/adverse-event-reporting>.

